This patient and observer blinded prospective randomized study will be performed on patients (aged 10 - 17years, both males and females, from all ethnic backgrounds) undergoing multilevel thoraco-lumbar spine surgery with instrumentation and fusion at Texas Children's Hospital, Houston, TX. After obtaining IRB (Institutional Review Board) approval and written informed consent from each patient or his or her legal representative, 56 patients scheduled for multilevel thoraco-lumbar spine surgery with instrumentation and fusion will randomly be assigned into two groups (control or treatment group) based on a computer generated random number using Random Allocation Software For Parallel Group Randomized Trials. There is an equal chance of being assigned to either group. The control group will be given placebo; whereas the treatment group will receive methadone 0.2 mg/kg intravenously.

Inclusion Criteria:

- 1) Patient age 10 \geq 17 years
- 2) Patients undergoing multilevel thoraco-lumbar spine surgery with instrumentation and fusion

Exclusion Criteria:

- 1) Preoperative methadone therapy
- 2) Inability to use the PCA
- 3) Allergy to methadone or morphine
- 4) Morbid obesity with a body mass index >36.0 kg/m²
- 5) Patients with chronic renal failure defined by serum creatinine >2.0 mg/dL
- 6) Liver failure defined as a history of cirrhosis or fulminant hepatic failure
- 7) Preoperative congenital heart disease or arrhythmias
- 8) Patient refusal to participate in study
- 9) Pregnancy (It is standard of care for all post menarche female patients to undergo a urine pregnancy test prior to surgery).

F2. Procedure

The perioperative management of patients will be in keeping with the current standard practices at Texas Children's Hospital. Before surgery, patients will be asked to rate their baseline pain using a verbal rating scale from 1 to 10 by a member of the research team. In addition, information on preoperative opioid consumption during the last 30 days will be collected.

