Postoperatively, patients will be asked to rate their pain using a validated pain scale (a verbal rating scale where 0 = no pain and 10 = worse pain ever) by a blinded research staff member. These pain scores will be collected at 1 hour after entry into recovery and every 4 hours during the first five days of hospitalization both at rest and during activity by the nurses. The cumulative intravenous opioid requirement at 24, 48, and 72 hour will be recorded. The cumulative breakthrough intravenous opioid requirement after initiation of oral pain medication will also be collected. The level of sedation will be determined using the University of Michigan Sedation Scale. In addition, complications such as the incidence of hypotension (defined as mean arterial blood pressure less than 50 mm Hg), the need for vasopressors, the incidence of respiratory depression (defined as a respiratory rate less than 8 breaths per minute, respiratory arrest, or the need for naloxone), the incidence of hypoxemia or desaturation (defined as oxygen saturation [Sao₂] less than 90% or the need for a supplemental oxygen to maintain Sao₂ greater than 94%), the incidence of cardiac arrhythmias, and the incidence of nausea and vomiting including the treatment of side effects will be also recorded. Upon discharge from the hospital, the patients will be asked to keep a diary consisting of daily opioid usage, episodes of nausea and vomiting, daily activity level, and satisfaction scores. As part of standard routine post-surgical followup in the orthopedic clinic, information is collected from the patients which consist of questionnaires regarding pain scores, functional status, activity level, and quality of life. The research team will collect this information at 3 months and 6 months postoperatively.

Section G: Sample Size/Data Analysis**G1. Sample Size**

How many subjects (or specimens, or charts) will be used in this study?

Local: 98

Worldwide: 98

Please indicate why you chose the sample size proposed:

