The primary endpoint of the study is the morphine consumption during the first 72 postoperative hours. The secondary outcomes include pain scores and the incidence of side effects such as respiratory depression, nausea, and vomiting. Continuous data including pain scores will be first examined for a normal distribution by the Shapiro χ Wilk test. The outcome variables between the two groups will be compared with Student's t -test where appropriate, for normally distributed continuous data or by nonparametric tests if the data were not normally distributed. It is anticipated that the distribution of pain scores will not be normal and that non-parametric tests will be required. Categorical data including patient gender, ASA physical status, incidence of side effects (respiratory depression, need for oxygen beyond the first 2 hours, nausea and vomiting) will be compared by Fisher's exact test. Analysis of variance for repeated measures will be performed to compare differences in pain scores between the treatment groups with time. Data will be presented as mean, standard deviation, median values or numbers (percentages). P values less than 0.05 will be considered statistically significant. In order to maintain a robust statistical analysis, we will also examine the differences in subjects with and without completely evaluable data in known factors that affect postoperative pain after spine surgery (e.g., age, gender, ASA physical status, duration of surgery, intraoperative opioids medications, time of the PACU stay, mean and peak pain scores and recorded opioid consumption in the PACU before discharge). Failure to show a difference in these factors may suggest that the missing data can be considered to be missing at random.

Section H: Potential Risks/Discomforts

H1. Potential Risks/Discomforts

Describe and assess any potential risks/discomforts; (physical, psychological, social, legal, or other) and assess the likelihood and seriousness of such risks:

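### Baseline pain and 30-day opioid use are collected but named in no analysis in G2, which gives up some available precision without biasing the comparison

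*Combined protocol and SAP*

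**What the plan says.** Two preoperative values are collected under F2 (Procedure). For pain, "patients will be asked to rate their baseline pain using a verbal rating scale from 1 to 10"; no anchors are given. For prior opioids, "information on preoperative opioid consumption during the last 30 days will be collected". After surgery, also under F2, pain is rated on "a verbal rating scale where 0 = no pain and 10 = worse pain ever".

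G2 (Data Analysis) sets the primary outcome: "The primary endpoint of the study is the morphine consumption during the first 72 postoperative hours". For the comparison of arms, "The outcome variables between the two groups will be compared with Student's" t-test, or by a nonparametric test if the data are not normal. For pain over time, "Analysis of variance for repeated measures will be performed to compare differences in pain scores between the treatment groups with time". Fisher's exact test covers categorical data.

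G2 also compares patients with and without fully evaluable data on "known factors that affect postoperative pain after spine surgery (e.g., age, gender, ASA physical status, duration of surgery, intraoperative opioids medications", continuing with "time of the PACU stay, mean and peak pain scores and recorded opioid consumption in the PACU before discharge". Neither baseline pain nor 30-day opioid use is on that list, and no other sentence of G2 gives either of them a role.

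**The concern.** Preoperative pain and prior opioid use are plausible predictors of postoperative pain and opioid need. The exclusion criteria in F1 remove only patients on preoperative methadone, so users of other opioids may enrol in a trial whose primary endpoint is opioid consumption. F1 describes no stratification. A covariate measured before treatment, already on file and related to the outcome, can narrow the confidence interval without recruiting anyone. Leaving it out also leaves any chance imbalance between the arms in the estimate.

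A smaller matter is the scale. As written, the baseline scale has no value for no pain. A pain-free patient would score 1 before surgery and could score 0 afterwards, and pain-free and minimal-pain patients would be merged in the covariate.

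**Working it through.** **Step 1: is a use of the baseline values named?** G2 plans four things: a t-test or nonparametric test, Fisher's exact test, repeated-measures ANOVA, and the comparison of evaluable with non-evaluable patients. None names baseline pain or 30-day opioid use as a covariate, stratifier, reference for change or balance check. The ANOVA time points are not listed and the factor list is open-ended. Use is therefore unspecified rather than ruled out.

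**Step 2: the plan's own design figure.** G1 gives a control mean of 275 mg, SD 75 mg, a target of 200 mg, 80% power, alpha 0.05 and 28 per group. The normal approximation, two-sided, gives n = 2 × (1.96 + 0.842)² × (75/75)² = 15.7, so 16 per group (17 by the exact t-test). The stated 28 is not reproduced. It matches 80% power only if the SD is about 98 to 100 mg. That is a separate matter, but it decides how much extra precision would be worth, so both SDs are carried forward.

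**Step 3: value of a covariate.** With correlation r between covariate and outcome, residual variance is multiplied by (1 − r²). The equivalent gain in sample size is 1/(1 − r²) − 1. Power at 28 per group is Φ(75 / [SD × √(1 − r²) × √(2/28)] − 1.96). The documents give no r; the values below are assumptions.

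| r | 1 − r² | Equivalent extra patients | 28 per group becomes | Power, SD 75 | Power, SD 100 |
|---|---|---|---|---|---|
| 0 | 1.00 | 0% | 28 | 96.3% | 80.1% |
| 0.1 | 0.99 | 1% | 28 | 96.4% | 80.5% |
| 0.3 | 0.91 | 10% | 26 | 97.5% | 83.7% |
| 0.5 | 0.75 | 33% | 21 | 99.1% | 90.0% |

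Estimating the slope has a small price. With 2 × 28 = 56 evaluable patients the expected variance rises by a factor of about 1 + 1/(56 − 4) = 1.019. At r = 0.1 the net factor is 0.99 × 1.019 = 1.009, so there is no gain. At r = 0.5 it is 0.75 × 1.019 = 0.764, equivalent to 1/0.764 − 1 = 31% more patients.

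**Step 4: chance imbalance.** With 28 per group, the 95% limits for the difference in covariate means are ±1.96 × √(2/28) = ±0.52 SD. The matching shift in the unadjusted primary difference is 0.52 × r × 75 mg: about 4 mg at r = 0.1, 12 mg at 0.3 and 20 mg at 0.5, against a target of 75 mg. With 49 per group the limits are ±1.96 × √(2/49) = ±0.40 SD, giving about 3, 9 and 15 mg.

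**Step 5: the scale.** A shift of 1 point for every patient has no effect on a linear covariate. Only the merging of 0 with 1 loses information. The documents give no baseline distribution. Assuming rounded-normal scores with a spread of about 2 to 2.5 points and 16% to 60% of patients pain-free, merging lowers the variance explained by 0.4 to 1.6 percentage points (out of 9) at r = 0.3, and by 1.1 to 4.4 (out of 25) at r = 0.5. A narrower spread would lose more.

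**The case against.** The strongest reply is that an unadjusted test in a randomised trial is valid. Its error rate already allows for chance imbalance, so omitting covariates is a choice and not an error. That stands. On the plan's stated inputs, 28 per group already gives about 96% power, so precision is not shown to be what limits the primary comparison. That also stands, subject to the SD of 75 mg being right. The correlations are assumed, and one range is applied to two different pairs: pain with pain, and prior opioids with postoperative opioids. If few patients took opioids before surgery, that covariate is nearly constant and contributes little.

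The change is also more than a sentence. G2 has no primary model to which a covariate could be added; it has a t-test or a rank test. It also expects pain scores to be non-normal.

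A reader might go further and infer that the two scales distort the treatment effect. The documents do not support this. No change-from-baseline analysis is planned, and both arms use the same baseline scale before treatment, so any distortion is equal in expectation. If baseline were entered in the ANOVA as a time point, the mismatch would affect the time effect, but G2 does not say that it is. The 1 to 10 wording may itself be a slip, since no anchors accompany it. Nor do the documents show that the baseline values will go unused, because the list of factors in G2 is open.

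**Conclusion.** The point holds as an optional improvement. The trial gathers two pre-treatment values and G2 assigns neither a role, so available precision may be given up. For an assumed r of 0.1 to 0.5 the reduction in residual variance is 1% to 25%, equivalent to about 1% to 33% more patients before the roughly 2% cost of estimating the slope. At the bottom of that range there is nothing to gain. For the primary endpoint the benefit is slight if the SD is 75 mg, with power already about 96%. It is more useful if the SD is nearer 100 mg, where power goes from 80% to between 81% and 90%. It may count for more in the pain scores, for which no power is stated.

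The mismatch of scales is a minor loss of information in a possible covariate. It is not a source of bias between the arms.

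**What to change.** In G2:

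- Analyse the primary opioid endpoint by ANCOVA: a linear model with treatment arm and 30-day preoperative opioid use. State in advance how prior use is coded, and that a transformed or rank-based version applies if the residuals are clearly non-normal.
- Include baseline pain as a covariate in the repeated-measures pain model, not as one of its time points.
- Keep the planned unadjusted t-test or nonparametric comparison as a sensitivity analysis.
- If the sponsor prefers not to adjust, say that both values are descriptive only.

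In F2, rate baseline pain on the same 0 to 10 scale, with the same anchors, as after surgery.

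No new data are needed. The cost is that a model and its handling of non-normal data must be fixed before analysis in place of a simple test, and that the return may be small, particularly if few patients used opioids before surgery.

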The aim of this study is to explore the efficacy of a single intra-operative dose of methadone in patients with idiopathic scoliosis undergoing multi-level posterior instrumentation and spinal fusion. The primary endpoints is the total opioid usage during POD (postoperative day) 0-4. Secondary endpoints include and pain scores during rest and with activity (getting out bed and ambulation) on POD 0-5 and side effects of pain medications

Section E: Protocol Risks/Subjects

E1. Risk Category

Category 2: Research involving greater than minimal risk, but presenting the prospect of direct benefit to the individual subjects.

E2. Subjects

Gender:
Both

Age:

Adolescent (13-17 yrs), Child (3-12 yrs)

Ethnicity:

All Ethnicities

Primary Language:

English, Spanish

Groups to be recruited will include:

Patients

Which if any of the following vulnerable populations will be recruited as subjects?

Children

Vulnerable populations require special protections. How will you obtain informed consent, protect subject confidentiality, and prevent undue coercion?

Patients presenting for spinal surgery will be identified from the Texas Children's Hospital operating room schedule that is routinely available to pediatric anesthesiologists. This will be cross referenced with the pediatric orthopedic surgeons' operative schedule as these cases are scheduled weeks to months in advance. The chart is reviewed to insure that the patient qualifies based on the inclusion and exclusion criteria.

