Postoperative Analgesia All groups: In keeping with current practice, supplemental oxygen will be available for oxygen saturations less than 94% during spontaneous ventilation. All patients will be monitored with continuous pulse oximetry as in keeping with practice at TCH. Every patient will have a patient controlled analgesia (PCA) morphine pump with a basal rate infusion of 0.01 mg/kg/hour, a demand dose 0.02 mg/kg with a lockout time of 10 minutes to be started in the PACU once the patient emerges from the anesthetic. The patient will be administered diazepam 0.05 mg/kg IV or oral with maximum of 5 mg every 6 hours as needed for muscle spasms in keeping with current practice. On POD 1, the basal rate of morphine will be discontinued and ketorolac 0.5 mg/kg every 6 hours initiated in keeping with current practices. On POD 3, the patient will be transitioned from the PCA with scheduled oral hydrocodone/acetaminophen at a dosage of 0.135 mg/kg of hydrocodone with a maximum of 15 mg every 4 hours in keeping with current practice. The PCA will be available for use during the transition for breakthrough pain.

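### Scheduled oral hydrocodone on POD 3 can fall inside the 72-hour morphine window, and the in-hospital opioid data listed are intravenous only

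*Combined protocol and SAP*

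**What the plan says.** All references are to the combined protocol and SAP.

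- **Switch to oral opioid (F2, postoperative analgesia).** "On POD 3, the patient will be transitioned from the PCA with scheduled oral hydrocodone/acetaminophen". The dose is "0.135 mg/kg of hydrocodone with a maximum of 15 mg every 4 hours in keeping with current practice". The paragraph is headed "Postoperative Analgesia All groups", so one rule covers both arms. Morphine PCA is not withdrawn at once: "The PCA will be available for use during the transition for breakthrough pain". No hour of the day or number of hours after surgery is attached to POD 3.
- **Data collected in hospital (F2).** "The cumulative intravenous opioid requirement at 24, 48, and 72 hour will be recorded", and "The cumulative breakthrough intravenous opioid requirement after initiation of oral pain medication will also be collected". Oral doses are not on the list. The patient diary, which does include daily opioid use, starts at discharge.
- **Primary endpoint, first statement (Section D).** "The primary endpoints is the total opioid usage during POD (postoperative day) 0-4".
- **Primary endpoint, second statement (G2).** "The primary endpoint of the study is the morphine consumption during the first 72 postoperative hours".
- **Planning figures (G1).** Control mean 275 mg, SD 75 mg, for opioid use over the first 3 days; target 200 mg; 28 per group. G1 does not say whether these figures cover intravenous opioid only.

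**The concern.** The endpoint in G2 runs on elapsed hours, while the change of opioid runs on a day label. Nothing in the plan ties one to the other. If POD 0 is the calendar day of surgery, hour 72 falls on POD 3 at the clock time when the postoperative period began. Any hydrocodone given earlier that day is then inside the window, is not counted, and replaces some PCA morphine that would have been counted. How much depends on when surgery ended, which has nothing to do with treatment.

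The gap is wider under Section D. Hydrocodone is the scheduled opioid on POD 3 and 4, so a total over POD 0-4 without it is not a total. H1 likewise describes the purpose as lowering total opioid consumption in hospital. An intravenous-only measure cannot support that statement, whatever the result.

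The actual oral start may also respond to nausea and vomiting, which the trial records as outcomes. If methadone changes these, oral start or intake could differ by arm and shift the morphine comparison either way. The plan names no oral data with which to see this.

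**Working it through.** **1. The plan's own figure.** Inputs from G1: difference 275 − 200 = 75 mg, SD 75 mg, alpha 0.05 (taken as two-sided), power 80%.

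n per group = 2 × (1.960 + 0.842)² × (75/75)² = 15.7, so 16.

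The stated 28 is not reproduced. That is a separate matter. It is relevant here only because 28 per group gives more power than the plan claims:

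power = Φ(Δ / (75 × √(2/28)) − 1.960) = Φ(75/20.04 − 1.960) = Φ(1.78) = 0.963.

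**2. Can the switch fall inside the window?**

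- *POD n = hours 24n to 24(n+1).* POD 3 starts at hour 72. Overlap is zero.
- *POD 0 = calendar day of surgery.* Overlap = clock time of PACU arrival minus clock time of the switch on POD 3, or zero if negative. The documents give neither time. Assuming arrival at 12:00-18:00 and a switch at 00:00-12:00, overlap runs from 0 h (12:00 − 12:00) to 18 h (18:00 − 00:00).

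**3. How much hydrocodone would go uncounted?** Doses = overlap / 4, rounded up. Dose = 0.135 mg/kg, capped at 15 mg. Weights and the conversion range of 0.25-0.5 mg IV morphine per mg oral hydrocodone are assumptions.

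- 50 kg, switch at 08:00, arrival 12:00-18:00: overlap 4-10 h, 1-3 doses of 6.75 mg, so 6.8-20.3 mg hydrocodone, or about 1.7-10.1 mg IV morphine equivalent.
- Upper end, 70 kg and 18 h: 5 doses of 9.45 mg = 47.3 mg, or up to 23.6 mg equivalent.
- Section D window, 50 kg, all of POD 3-4: 48 h / 4 h = 12 doses × 6.75 = 81 mg, or about 20-41 mg equivalent.

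**4. Effect on the comparison when both arms switch alike.** Suppose the last h hours contribute no difference, use is flat over the window, and the SD stays at 75 mg. Then Δ = 75 × (72 − h)/72.

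| h lost in both arms | Δ (mg) | Δ/20.04 − 1.960 | Power at 28 per group |
|---|---|---|---|
| 0 | 75.0 | 1.78 | 0.963 |
| 4 | 70.8 | 1.57 | 0.942 |
| 8 | 66.7 | 1.37 | 0.914 |
| 10 | 64.6 | 1.26 | 0.897 |
| 18 | 56.2 | 0.85 | 0.801 |

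The extra variance from differing surgery end times is not included, because the documents give nothing to size it with.

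**5. Effect when the arms switch at different times.** The ceiling per hour of difference is 275/72 = 3.8 mg, about 5% of 75 mg. It assumes that oral dosing displaces PCA morphine completely and that use on POD 3 equals the 72-hour average.

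**The case against.** A reader might infer that the overlap is a fact, that a change of route will therefore be reported as opioid sparing, and that the oral contribution is lost for good. The documents do not support any of the three.

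- **Overlap.** POD is not defined in hours. G1 describes the planning quantity by days and G2 by 72 hours, which fits a window meant to close as the switch begins. Overlap is possible, not established.
- **False sparing.** The switch is scheduled, weight-based and the same in both arms. Patients, the intra-operative anesthesiologist and the staff who collect PCA use are blinded (F1, F2). A loss common to both arms shrinks the difference and does not create one. F2 states no oral-tolerance criterion for the switch, so a nausea-driven difference in timing is plausible but is an inference.
- **Large spurious effects.** Multiplying the hourly ceiling by 12 gives 46 mg, or 61% of the target difference. That needs a 12-hour average gap in switch time between randomised arms and full displacement although the PCA stays available. It also needs a flat rate, although the basal infusion stops and ketorolac starts on POD 1. It stacks upper bounds and should not be relied on.
- **Lost data.** Section K allows medication information from health records, and collecting IV breakthrough use after oral start requires knowing when oral dosing began. The supportable statement is that oral doses are not listed as collected, not that they cannot be recovered.

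The IV totals at 24 and 48 hours also precede any calendar POD 3 and give a partial check.

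All of this stands, and it limits the size and direction of the problem. It does not supply the missing oral item, the conversion or the POD definition, and it does not help Section D's endpoint.

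**Conclusion.** The concern holds as a gap in measurement and definition. Under a calendar-day reading, scheduled hydrocodone can enter the 72-hour window and is not counted; under an hours-72-to-96 reading it cannot. On both readings, total opioid over POD 0-4 cannot be built from the items F2 lists.

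For the G2 endpoint the expected consequence is modest and conservative. An 8-hour common loss reduces the detectable difference from 75 to 66.7 mg and power from 0.963 to 0.914. Even the 18-hour extreme leaves 0.801, given 28 evaluable patients per group, a flat rate and an unchanged SD. Bias in either direction needs oral start or intake to differ by arm. The listed items would not show whether this happened.

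The larger consequence is for interpretation: a lower IV morphine total, taken alone, would not show lower total opioid use, which is what Section D and H1 set out to study. The clock times, weights and conversion range above are assumptions, not figures from the documents.

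**What to change.** - **F2:** add every in-hospital oral opioid dose, in mg with its time, extracted from the medication record.
- **G2:** define POD against hours after surgery for analysis purposes, and reconcile the Section D and G2 endpoints into one measure and one window.
- **G2:** analyse total opioid, intravenous plus oral, in IV morphine equivalents, with a prespecified conversion factor and a range of factors as sensitivity analysis.
- **G2:** report time of first oral dose by arm.
- **G2:** use the IV total at 48 hours, already recorded, as a sensitivity analysis. It should not become the primary, because G1's 275 mg (SD 75 mg) refers to 3 days and the documents give no 48-hour mean or SD.

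The clinical schedule is unchanged. The cost is some chart extraction, a few sentences in G2, and reliance on a conversion factor, which the sensitivity range is there to expose.

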The sample size was based on the assumption that opioid use in the first 3 days in the placebo group would be similar to that in a previously published study of the same patient population undergoing spine surgery (mean 275 mg SD 75 mg). A group size of 28 would be required for an 80% power of detecting a 30% reduction in opioid use from 275 to 200 mg at the 0.05 level of significance. Allowing for a 50% dropout rate for incomplete data, we will recruit 49 patients in each group for a total of 98 subjects.

G2. Data Analysis

Provide a description of your plan for data analysis. State the types of comparisons you plan (e.g. comparison of means, comparison of proportions, regressions, analysis of variance). Which is the PRIMARY comparison/analysis? How will the analyses proposed relate to the primary purposes of your study?

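### The sample-size figures do not agree: 28 per group gives 96% power rather than 80%, 49 per group does not keep 28 after 50% loss, and F1 randomises 56 patients where G1 recruits 98

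*Combined protocol and SAP*

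**What the plan says.** Section G1 (Sample Size) takes its placebo assumption for opioid use in the first three days from an earlier published study: "mean 275 mg SD 75 mg". The target effect is "detecting a 30% reduction in opioid use from 275 to 200 mg", tested "at the 0.05 level of significance", and the stated requirement is "A group size of 28 would be required for an 80% power of detecting a 30% reduction in opioid use". It continues: "Allowing for a 50% dropout rate for incomplete data, we will recruit 49 patients in each group for a total of 98 subjects". The subject-count field of G1 also gives 98, both local and worldwide.

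Section F1 (Design) gives a different total: "56 patients scheduled for multilevel thoraco-lumbar spine surgery with instrumentation and fusion will randomly be assigned into two groups", with equal allocation. Section G2 (Data Analysis) compares the groups by Student's t-test, or by a nonparametric test if the data are not normal. It plans no multiplicity adjustment.

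**The concern.** G1 supplies every input to a standard two-group calculation except the sidedness of the test, so its result can be checked directly. An effect of one full standard deviation is large, and 28 per group is well above what 80% power for it requires. The dropout step looks wrong too, because halving 49 gives fewer than 28. The 56 in F1 is twice 28, yet F1 states it as the number randomised.

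The evaluable number, the power, the loss allowance and the randomised total therefore cannot all be true. The background section gives the lack of an adequately powered study as the reason for this trial, so the power statement is central. The subjects are children, and the protocol classes the study as greater than minimal risk, so the number enrolled needs a justification that follows from its own inputs. F1 and G1 differ by 98 − 56 = 42 children, which leaves the length of the allocation list and the point at which enrolment stops uncertain.

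**Working it through.** **Inputs.** From G1: placebo mean 275 mg, treated mean 200 mg, SD 75 mg, α = 0.05, power 80%, 28 per group, 50% dropout, 49 per group recruited. From F1: 1:1 allocation, 56 randomised. From G2: t-test or nonparametric alternative. Sidedness is not stated; I take two-sided and also try one-sided.

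**1. Effect size.** Difference = 275 − 200 = 75 mg. Standardised effect d = 75/75 = 1.0. Relative reduction = 75/275 = 27.3%. A literal 30% reduction would be 82.5 mg (to 192.5 mg), d = 82.5/75 = 1.1.

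**2. Trying to reproduce 28 per group.** Normal approximation: n = 2(z₀.₉₇₅ + z₀.₈₀)²/d² = 2(1.960 + 0.842)²/1² = 15.7, so 16 per group. The noncentral t calculation gives 16.7, so 17 per group. The stated 28 does not reproduce, and these alternative readings do not recover it:

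| Reading (80% power) | Per group |
|---|---|
| Two-sided t-test, 75 mg | 17 |
| One-sided t-test, 75 mg | 14 |
| Two-sided t-test, 82.5 mg (true 30%) | 14.002, strictly 15 |
| Two-sided, 75 mg, worst-case Wilcoxon efficiency: 16.7/0.864 = 19.3 | 20 |
| Two-sided, 75 mg, Bonferroni for five tests | 26 |

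**3. Power at the numbers in play** (two-sided t-test, 75 mg, SD 75 mg):

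| Evaluable per group | Power |
|---|---|
| 14 | 72.1% |
| 17 | 80.7% |
| 24 | 92.4% |
| 25 | 93.4% |
| 28 | 95.7% |

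**4. What 28 per group would fit.** At 80% power, 28 per group detects d = 0.762. With SD 75 mg that is 0.762 × 75 = 57 mg, or 57.2/275 = 20.8%. If the difference stays at 75 mg, the SD must be 75/0.762 = 98 mg.

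**5. Dropout.** To keep 28 after 50% loss: 28/(1 − 0.5) = 56 per group, 112 in total. With 49 per group: 49 × 0.5 = 24.5 evaluable. The loss that 49 can absorb while keeping 28 is 1 − 28/49 = 42.9%. The common shortcut of adding 50% gives 28 × 1.5 = 42, which is not 49 either. Starting from the 17 that the inputs support: 17/0.5 = 34 per group, 68 in total.

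**6. Consequence of each way of resolving the conflict** (two-sided t-test, 75 mg difference, 50% loss):

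| Randomised | Evaluable per group | Power, SD 75 mg | Power, SD about 98 mg |
|---|---|---|---|
| 98 (G1) | 24 to 25 | 92% to 93% | 73% to 75% |
| 56 (F1) | 14 | 72% | about 49% |

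**The case against.** The strongest reply is that the errors run mostly in a safe direction. On the stated inputs, 98 randomised with the full 50% loss leaves 24 or 25 per group and 92% to 93% power, above the 80% sought. The dropout shortfall exists only against 28; against 17, recruiting 49 per group is more than enough. This stands, with one limit: it assumes that SD 75 mg is right and 28 is wrong, and the protocol does not say which. If 28 came from a larger SD, the same 98 patients fall short of 80%.

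A second reply is that 98 is plainly the intended total. G1 is the dedicated sample-size field, gives 98 more than once and explains it by dropout, while 56 equals 2 × 28 and looks like a pre-dropout figure left in F1. I agree that 98 is better supported. F1 nevertheless gives 56 as the number to be randomised, in current text, and that has to be corrected. It also follows that the 72% figure combines F1's total with G1's loss rate, a combination the protocol does not set out; it applies only if 56 is taken as final.

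Two smaller points are fair. Calling 27.3% a 30% reduction could be loose rounding, since the absolute values define the effect. And although a true 30% fall needs about 14 per group, or 28 in total, the idea that a total was mislabelled as a group size is conjecture and nothing here depends on it.

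**Conclusion.** The concern holds in all three parts and needs correction. With a 75 mg difference, SD 75 mg and a two-sided 5% t-test, 80% power needs 17 per group, and the stated 28 gives 95.7%. Recruiting 49 per group does not preserve 28 after 50% loss; it covers a loss of at most 42.9%. F1 and G1 differ by 42 patients on the number enrolled.

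This does not show that the trial is underpowered: at 98 randomised and SD 75 mg, power after 50% loss is about 92%. That reassurance depends on the SD. If the true planning SD was about 98 mg, which is what 28 per group at 80% power for 75 mg implies, power after 50% loss is about 73% to 75%. Only the sponsor can say which figure was intended. Leaving sidedness unstated does not change the conclusion, because a one-sided test moves the requirement further from 28.

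**What to change.** Restate G1 so that each figure follows from the one before:

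- Describe 275 to 200 mg as a 27% reduction, and state that the test is two-sided if that is intended.
- Either give 17 evaluable per group as the requirement for 80% power at SD 75 mg, or keep 28 and say what it provides: 96% power for 75 mg, or 80% power for 57 mg (21%). If 28 came from a larger SD (about 98 mg), state that SD and its source.
- Either say that 98 randomised with 50% loss yields about 24 evaluable per group (92% power at SD 75 mg), or replace 50% with the 43% loss that 49 per group covers while keeping 28. If the SD proves to be about 98 mg, the first option must report the lower power in its place.
- Use one randomised total in F1 and G1. If 98 stands, amend F1, and if 56 is meant as the evaluable target, label it so.

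The cost is one recalculation and edits to two sections. No extra patients are needed to make the document consistent.
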